6.5. Negative dengue case

For early and late presenters, a negative dengue case is a participant with a negative result for all planned laboratory tests on both acute and convalescent samples.

6.6. Indeterminate dengue case

An indeterminate dengue case is a participant evaluated as an SDC (Section 6.1) and not classified as laboratory confirmed case (Section 6.2), probable case (Section 6.4) or negative case (Section 6.5).

6.7. Primary symptomatic dengue case

A primary symptomatic dengue case is a subject with laboratory confirmed or probable symptomatic dengue infection and without evidence of previous dengue infection (absence of Ig G antibodies at the previous scheduled visit and absence of laboratory-confirmed symptomatic case detected previously at study surveillance).

6.8. Secondary symptomatic dengue case

A secondary symptomatic dengue case is a subject with laboratory confirmed or probable symptomatic dengue infection and with evidence of previous dengue infection (presence of IgG antibodies at the previous scheduled visit(s) or laboratory-confirmed symptomatic case detected previously at study surveillance).

6.9. Primary inapparent dengue infection

This condition is defined as a documented seroconversion (anti-dengue IgG antibodies) between two sequential sera samples obtained during the scheduled visits without clinical suspicion of dengue (identified during the time period in which seroconversion occurred).

6.10. Previous dengue infection

A subject will be considered as having previous dengue infection at visit 1(baseline) based on seroprevalence at visit 1, namely if:

- Dengue IgG positive (ie reactive) at visit 1 (baseline) or
- Laboratory-confirmed symptomatic dengue case detected at visit 1 (baseline)

A subject will be considered as having previous dengue infection at any time after visit 1 (baseline), if:

- Dengue IgG positive (ie reactive) at previous schedule visit(s) or
- Laboratory-confirmed symptomatic dengue case detected previously at study surveillance

This status will be considered as unknown for subjects without laboratory result at baseline Visit 1.

7. STATISTICAL ANALYSES

Note that data derivation rules are described in Section 11 and will not be repeated below.

Continuous variables will be summarized with number of non-missing observations, mean, standard deviation (SD), median, minimum, maximum, 25th and 75th percentiles. Categorical variables will be summarized with frequency tables; numbers and percentages for each level will be given.

If an elimination code 900 is attributed, then all the analyses planned to be done on the Total cohort will be done on the Total cohort without subjects with code 900, except Template 5 from EPI-DENGUE-006 BOD BR (116606) TFL (Final analysis) (14-JUN-2019) DRAFT.

The final analysis will be performed on the following study sites using data up to the specified study visits and dengue seasons covered up to study termination:

Region/Study sites name	Initial / Expansion / Replacement cohort	Subject numbers	Study visits covered up to study termination	Dengue season covered up to study termination
Rio	Initial	P - PP	Visit 1 to Visit 6	2015, 2016, 2017, 2018
	Replacement*	PP - PP	Visit 1 to Visit 4	2016, 2017, 2018
Manaus	Initial	PPD - PPD	Visit 1 to Visit 6	2015, 2016, 2017, 2018
	Replacement*	PPD - PPD	Visit 1 to Visit 2	2018
Salvador	Initial	PPD - PPD	Visit 1 to Visit 5	2016, 2017, 2018
Natal	Expansion	PPD - PPD	Visit 1 to Visit 3	2017, 2018
Campinas	Expansion	PPD - PPD	Visit 1 to Visit 2	2018

*only 1 replacement cohort

The following results will be available at the scheduled visits for the following tests:

- Dengue IgG ELISA will be available at Visit 1
- For Visit 2 onwards, Dengue IgG ELISA will be available for subjects with IgG negative at the previous visit.

The following results will be available in case of SDC, for the following tests:

Assays	Result type	Early presenters		Late presenters	
		Acute sample (first visit)	Convalescent sample (follow-up visit)	Acute sample (first visit)	Convalescent sample (follow-up visit)
RT-qPCR	Positive, negative or not typeable DENV type Copies/ml Final classification into positive or negative (used for the dengue case classification)	Yes	TNP	TNP	TNP
NS1 ELISA	Reactive or no reactive	Yes	TNP	Yes	TNP
Dengue IgM ELISA	Reactive or no reactive	Yes	Yes	Yes	Yes
Dengue capture IgG ELISA	Reactive or no reactive	TNP	Yes	Yes	Yes
Hematology / Biochemistry	Numerical results	Yes	TNP	Yes	TNP

TNP = test not performed on the sample as per protocol

Laboratory results ‘Not reactive’ and ‘Reactive’ for NS1, Dengue IgM and Dengue capture IgG ELISA tests will be considered as ‘Negative’ and ‘Positive’ respectively for the classification of the SDC (refer to Section 6).

If a blood sample is collected for more than 1 SDC, the following rule will be applied:

- The sample collected from start of the SDC (first symptom onset) and the day before onset of the next SDC will be used to associate the blood sample to a SDC.

7.1. Analysis of demographics/baseline characteristics

7.1.1. Analysis as planned per protocol

Socio-demographic and patient characteristics (e.g., age at study enrolment, gender, household conditions, medical history and vaccination history) will be summarized overall and by region, and at the beginning of each season using descriptive statistics.

7.1.2. Additional considerations

The number of subjects enrolled into the study will be tabulated by study site and overall on the Total cohort.

The number of subjects enrolled per household will be tabulated by study site and overall on the Total cohort.

The numbers of withdrawn subjects will be tabulated according to the reason for withdrawal by study site and overall on the Total cohort.

The distribution of the subjects in the ATP cohort and reasons for exclusion will be tabulated by study site and overall.

Demographic characteristics (age at Visit 1, age category at visit 1: < 1 year, 1-4 year, 5-8 year, 9-17 year, 18-49 year, >= 50 years, seroprevalence at visit 1 and gender) will be summarized using descriptive statistics by study site and overall on the ATP cohort.

Socio-economic characteristics of the households at Visit 1 (enrolment visit) will be tabulated by study site and overall on the ATP cohort.

The planned analysis of medical and vaccination history was removed.

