Currently, haematology testing (HCT, CBC) is planned to be performed for all suspected dengue cases at the initial visit, regardless of the time between fever onset and the visit. However, for patients presenting more than 14 days after fever and/or rash onset, the relevance of these tests is low. Therefore, a maximum interval will be defined in this amendment.

The geographical distribution of the participants may impact the risk of infection. Therefore, updating information on the household of the study participants and their location at yearly visits is important during the follow-up period (which may extend to 4 years). Hence, socio-demographic and household information will be collected at yearly visits.

Some sites may have more than 500 active participants enrolled in the penultimate year of the study. However, their site may have experience with high drop-out rate and can expect to drop below 500 participants during the last year of the study. To address this challenge, criteria to allow for replacement cohort recruitment was clarified.

Also, the NS1 test has been removed for the late presenters since this test does not have clinical relevance in the case of late presenters.

Collection of dengue vaccination history has been added since a competitor dengue vaccine is currently available in the Brazilian market.

Protocol Amendment 4 Investigator Agreement

I agree:

- To conduct the study in compliance with this protocol, any mutually agreed future protocol amendments or protocol administrative changes, and with any other study conduct procedures and/or study conduct documents provided by GlaxoSmithKline Biologicals (GSK Biologicals)
- To assume responsibility for the proper conduct of the study at this site
- That I am aware of, and will comply with, 'Good Clinical Practice' (GCP) and all applicable regulatory requirements
- To ensure that all persons assisting me with the study are adequately informed about study-related duties and functions as described in the protocol
- To acquire the reference ranges for laboratory tests performed locally and, if required by local regulations, obtain the laboratory's current certification or Quality Assurance procedure manual.
- To ensure that no samples (including serum samples) are retained onsite or elsewhere without the approval of GSK Biologicals and the express written informed consent of the subject and/or the subject's legally authorized representative.

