Prematurely terminate participation	A subject who is withdrawn from the study by the investigator or who decides to stop participation before the time he/she had to be in the study.
Primary dengue infection	The first dengue infection experienced by a subject is qualified as primary while subsequent infections (second, third or fourth) are qualified as secondary.
Prospective study:	A study in which the subjects/cases are identified and then followed forward in time in order to address one or more study endpoints
Replacement subjects	Subjects who will be enrolled to compensate for subjects: 
• from the initial cohort: who will not want to extend participation for three additional years or• from the initial and expansion cohorts: who prematurely terminate participation or subjects lost to follow-up.
Research protocol:	A document that describes the objective(s), design, methodology, statistical considerations, and organization of a trial. The protocol usually also gives the background and rationale for the trial, but these could be provided in other protocol referenced documents
Seroconversion:	Documented positive antibody test with previous documented negative antibody test.
Site Monitor:	An individual assigned by the sponsor who is responsible for assuring proper conduct of clinical/ epidemiology studies at one or more investigational sites
Study population:	Enrolled members of a sample of the population of interest

CONFIDENTIAL

116606 (EPI-DENGUE-006 BOD BR)
Protocol Amendment 4 Final

- Subject:** Term used throughout the protocol to denote an individual who has been contacted in order to participate or participates in the clinical/ epidemiology study, or a person about whom some medical information has been recorded in a database
- Subject number:** A unique number identifying a subject, assigned to each subject consenting to participate in the study
- Surveillance:** Surveillance is defined as the on-going systematic collection, collation, analysis, and interpretation of descriptive epidemiological health data on a specific disease. Surveillance can monitor incidence and/or prevalence, and/or inform about when and where health problems are occurring and who is affected.

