5.5.2.2. Collect specific medical history data (Amended 16 October 2017)

A baseline medical history, including history of dengue infection, *Zika and chikungunya infection, and YF and dengue vaccination history will be taken*. Results will be recorded in the subject's source document for subsequent recording in the eCRF.

YF *and dengue* vaccination status will be recorded, along with the source of the information (either written or oral record). A vaccination record, if available, is preferable but self-reported history will be recorded if the vaccination record is not available.

Information on medical history (e.g., diabetes, cardiovascular diseases, asthma, cancers, hematologic diseases, genetic disorders) will be collected.

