1. DOCUMENT HISTORY

Date	Description	Protocol Version
29-OCT-2019	Amendment 1*	Amendment 4: 16 Oct 2017
14-JUN-2019	Final version	Amendment 3: 09 JAN 2015

[figure not shown]
- * In 2017 GSK vaccines has decided to terminate the development of a dengue vaccine. Accordingly none of the tertiary objectives will be evaluated and the analyses additional to those planned in the protocol have been removed from the first statistical analysis plan. In addition in light of the low number of dengue episodes, the large number of positive anti-dengue IgG at visit 1 and the number of dengue cases reported outside the season,
- (1) The analyses of PCR confirmed cases (only 10 cases) and the analyses of secondary dengue infections were removed.
 - (2) The analyses by seroprevalence at each visit were removed,
 - (3) The analyses by season were removed. Only the analyses by calendar year are to be conducted
 - (4) Subjects without seroprevalence status at visit 1 were removed from the ATP cohort because serological status of symptomatic/inapparent dengue infections cannot be assessed properly for such subjects
 - (5) Planned analyses of medical and vaccination history were removed.
 - (6) The statistical method was updated to ignore the household cluster effect and to provide incidence rate with confidence interval in absence of dengue episodes in a calendar year for a study site .

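### The IgG-based definitions of inapparent and previous dengue infection take no account of the dengue vaccination history that the protocol collects

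*SAP*

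**What the plan says.** **Collection.** The rationale for Protocol Amendment 4 states: "Collection of dengue vaccination history has been added since a competitor dengue vaccine is currently available in the Brazilian market". Protocol section 5.5.2.2 covers yellow fever and dengue together and says that "vaccination status will be recorded, along with the source of the information (either written or oral record". A vaccination card is preferred and self-report is accepted without one. Section 5.5.3 and Tables 2 to 4 call for updates at later scheduled visits.

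**Classification.** SAP Amendment 1 names Protocol Amendment 4 as its basis. Section 6.9 opens "This condition is defined as a documented seroconversion (anti-dengue IgG antibodies" and requires the change to occur "between two sequential sera samples obtained during the scheduled visits without clinical suspicion of dengue (identified during the time period in which seroconversion occurred". The protocol glossary defines seroconversion as "Documented positive antibody test with previous documented negative antibody test". In SAP Table 1 the inapparent-infection numerator is everyone IgG positive at the visit, over everyone IgG negative at the visit before. Section 6.10 assigns previous infection if a subject is "Dengue IgG positive (ie reactive) at visit 1 (baseline", or has a laboratory-confirmed case at that visit. A parallel rule applies after Visit 1.

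**Reporting.** SAP section 7.1.2 states "The planned analysis of medical and vaccination history was removed", and the change list in SAP section 1 repeats it: "Planned analyses of medical and vaccination history were removed".

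**The concern.** The sponsor collects the one variable that could separate a vaccine response from an infection, and no rule uses it. A subject who is IgG negative at one scheduled visit, receives a dengue vaccine, and is IgG reactive at the next without a suspected episode meets section 6.9 as written. A reactive subject vaccinated before Visit 1 meets section 6.10 as written. Misclassification of this kind goes only one way: it adds to the count of infections.

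Inapparent infection and Visit 1 seroprevalence are both secondary objectives in SAP section 3.2, and the study is meant to inform attack-rate assumptions for vaccine trials. An inapparent-infection figure that included vaccine responses would overstate exposure. The protocol accepts the principle elsewhere: the Amendment 4 rationale asks that dengue serology be read with Zika cross-reaction in mind. Vaccine-induced antibody calls for the same care.

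**Working it through.** The plan gives no figure to reproduce here, so the check is a trace of the variable followed by an illustration of size.

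**Step 1. Where dengue vaccination enters the plan**

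| Stage | Place | Dengue vaccination mentioned? |
|---|---|---|
| Collection | Protocol 5.5.2.2, 5.5.3, Tables 2–4 | Yes |
| Exclusion criteria | Protocol 4.5 | No |
| ATP elimination codes 900, 2010, 2020 | SAP 5.1, 5.2.2 | No |
| Inapparent infection | SAP 6.9, Table 1 | No |
| Previous infection | SAP 6.10 | No |
| Baseline summary of vaccination history | SAP 7.1.2 | Removed |
| Risk-factor analysis (tertiary) | SAP 7.4 | Not analysed |

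**Step 2. What is still reported.** Primary inapparent infection remains a secondary endpoint (SAP 4.2) and a laboratory-diagnosis category (SAP 7.3.2). Seroprevalence is summarized at Visit 1 (SAP 7.2.2.2). A primary-dengue descriptor remains in SAP 7.3.2. Analyses of secondary infections and by seroprevalence at each visit were dropped (SAP 7.2.2.1).

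**Step 3. Inapparent infection: illustration only.** Let p be the true inapparent proportion among IgG negatives in an interval, v the share of them vaccinated in that interval, and s the probability that vaccination makes the ELISA reactive. The documents give none of the three. With infection and vaccination taken as independent:

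observed = 1 − (1 − p)(1 − v·s)

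| p | v | s | Observed | Ratio to p |
|---|---|---|---|---|
| 5% | 0.5% | 0.5 | 1 − 0.95 × 0.9975 = 5.24% | 1.05 |
| 5% | 1% | 0.8 | 1 − 0.95 × 0.992 = 5.76% | 1.15 |
| 3% | 1% | 1 | 1 − 0.97 × 0.99 = 3.97% | 1.32 |
| 5% | 5% | 0.8 | 1 − 0.95 × 0.96 = 8.80% | 1.76 |
| 1% | 5% | 1 | 1 − 0.99 × 0.95 = 5.95% | 5.95 |

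For p from 1% to 5%, v from 0.5% to 5% and s from 0.5 to 1, the ratio runs from 1.05 to 5.95. If v = 0 the ratio is 1. The ratio equals 1 + v·s·(1 − p)/p, so it depends on shares and not on the number at risk. A small risk set matters only because each vaccinee is then a larger share.

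**Step 4. Visit 1 seroprevalence.** Replace p by the true seroprevalence and let v be the share vaccinated among the never infected, with s = 1. At 80% and v = 0.5%: 1 − 0.20 × 0.995 = 80.1%, up 0.1 points. At 60% and v = 5%: 1 − 0.40 × 0.95 = 62.0%, up 2.0 points. These inputs are also assumed.

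Timing narrows this further. The documents first mention a marketed vaccine in Amendment 4 (16 October 2017). In SAP section 7, the first season covered is 2015 for the initial Rio and Manaus cohorts, 2016 for Salvador and the Rio replacements, and 2017 for Natal. Only Campinas and the Manaus replacements begin with 2018.

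**Step 5. Primary endpoint.** SAP section 6.2 requires RT-qPCR, NS1 or IgM seroconversion in a suspected case (IgM seroconversion alone for late presenters). IgG does not enter.

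**The case against.** The strongest reply is that the deleted analysis was only a descriptive baseline summary (Protocol 8.5.1). It fed no case definition, so its removal changed no classification. The superseded SAP of June 2019 named only yellow fever vaccination, so no named dengue-vaccination analysis was lost. This stands. A reader might infer that SAP 7.1.2 causes the misclassification; it does not. The gap is in sections 6.9 and 6.10 and Table 1, and the protocol's own definitions (5.7.1.5, 5.7.1.8) have it too. The removal matters only because the summary could have shown the extent.

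Second, nothing in the documents gives vaccine uptake in the cohort or says that vaccination makes this ELISA reactive. A reader might infer that both estimates are biased upward as a fact. The documents support only that they may be.

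Third, a reader might infer that most subjects were IgG positive at Visit 1. The SAP says only that the number was large and gives no proportion.

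Fourth, the consequences for exposure class have largely gone, since the secondary-infection and by-visit seroprevalence analyses were removed. What remains is the primary-dengue descriptor.

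Fifth, vaccination history before Amendment 4 was not collected prospectively, so censoring recorded vaccinees would act unevenly over time and sites. This is a real limit. It is eased in part because the item is a history, updated at scheduled visits up to the one after the 2018 season.

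None of this answers the core point: a recorded vaccinee who seroconverts is counted as infected under the plan's own rule. The reasons given for the SAP changes (few episodes, many Visit 1 positives, out-of-season cases) do not bear on vaccination.

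**Conclusion.** The point holds as a conditional one about definitions. If any IgG-negative subjects were vaccinated during follow-up, and if vaccination makes the IgG ELISA reactive, the inapparent-infection estimate may be too high. Its size cannot be computed from the documents. The range of 1.05 to 5.95 times the true value shows only how strongly the answer depends on unknown inputs, and should not be read as an estimate of bias in this study.

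Visit 1 seroprevalence is probably affected little (0.1 to 2.0 points under the assumptions shown) and mainly in late enrolments. The primary endpoint is little exposed. All analyses are descriptive, so no test or decision rule is at risk. This is a low-cost improvement to a retained secondary endpoint and does not undermine the main result.

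**What to change.** 1. Tabulate subjects with recorded dengue vaccination by site and visit, with the source of the information. If the count is zero, one sentence in the report closes the point for recorded vaccination.
2. Censor recorded vaccinees from the inapparent-infection risk set at the recorded vaccination date. Because Table 1 works by visit interval, this means dropping the interval containing that date, and all later ones, from both numerator and denominator, whatever the IgG result.
3. Label IgG-positive subjects vaccinated before Visit 1 separately in the seroprevalence table and in the primary-dengue descriptor.
4. Show results with and without these changes.
5. State that dengue vaccination history was collected only from Amendment 4 (16 October 2017), is partly self-reported, and may be unevenly complete across sites and calendar time.

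The cost is one derived flag and a few extra table rows from data already collected; no new sampling is needed. Two limits remain. Incomplete history means some vaccinees will stay uncensored, so the corrected estimate may still be somewhat high, and unevenly so. Also, section 5.5.2.2 asks for status and source but does not mention a vaccination date. Where none was recorded, the SAP should state how the interval is assigned, for example from the visit at which vaccination was first reported.

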7.2. Analysis of primary and secondary endpoints

7.2.1. Analysis as planned per protocol

The following analyses will be performed overall and by DENV type, study site, gender and age-group previous dengue exposure (Yes = DENV IgG antibodies at previous visit and No = no DENV IgG antibodies at previous visit):

- Incidence rate of *laboratory-confirmed symptomatic dengue infection* with 95% CI for each season separately: the numerator will be the number of subjects with lab-confirmed symptomatic dengue infection during the season (between the visits scheduled before and after the season). The denominator will be the total person-years at risk, i.e. from the visit scheduled before the season until the first RT-qPCR confirmed symptomatic dengue infection during the season, the next scheduled visit or the subject's withdrawal, whichever comes first.

- Incidence rate of *laboratory-confirmed symptomatic dengue infection* with 95% CI all seasons combined: the numerator will be the number of subjects with lab-confirmed symptomatic dengue infection during the study period. The denominator will be the total person-years at risk, i.e. from enrolment until the first RT-qPCR confirmed symptomatic dengue infection, the end of the study or the subject's withdrawal, whichever comes first.

The following analyses will be performed by study site, gender and age-group previous dengue exposure (primary or secondary):

- Incidence rate of *laboratory confirmed or probable symptomatic dengue infections* with 95% CI for each season separately and overall. The numerator will be the number of subjects with symptomatic dengue infection (including laboratory-confirmed and probable cases) during the period. The denominator will be the total person-years at risk.
- Incidence rate of *probable symptomatic dengue infection* with 95% CI for each season separately and overall. The numerator will be the number of subjects with probable symptomatic dengue infection. The denominator will be the total person-years at risk.

The following analyses will be performed by study site, gender and age-group:

- The proportion of subjects with *primary inapparent dengue infection* at each subsequent scheduled visit (not at enrolment) with 95% CI will be calculated as the number of dengue IgG positive cases and at the visit divided by the total number of subjects IgG negative at the previous visit.
- The proportion of subjects with *secondary symptomatic dengue infection (probable or confirmed)* at each subsequent scheduled visit (not at enrolment) with 95% CI will be calculated as the number of subjects with secondary symptomatic infection since the previous visit divided by the total number of IgG positive subjects at the previous visit.
- The (crude) *seroprevalence of dengue infection* will be calculated at enrolment and at each scheduled visit as a proportion (i.e., the number of dengue IgG positive subjects tested positive at this visit or known to be positive from previous visits divided by the total number of subjects for whom dengue IgG serostatus is known).

Endpoint numerators and denominators are described in [Table 1](#) below:

Table 1 Numerators and Denominators within each strata (DENV type, study site, gender and age-group and previous dengue exposure (primary or secondary))

Analysis	Numerator	Denominator
Incidence rate of laboratory confirmed symptomatic infection by year	All confirmed acute cases during the season (between the visits scheduled before and after the season)	Total person-years at risk, i.e. from the visit scheduled before the season until the first RT-qPCR confirmed symptomatic dengue infection during the season, the next scheduled visit or withdrawal, whichever comes first.
Incidence rate of laboratory-confirmed symptomatic dengue infection for all seasons combined	All confirmed acute cases during the study period	Total person-years at risk, i.e. from enrolment until the first RT-qPCR confirmed symptomatic dengue infection, the end of the study or withdrawal, whichever comes first.
Incidence rate of laboratory confirmed or probable symptomatic dengue infections	All symptomatic dengue infections (including laboratory-confirmed and probable cases) during the period.	Total person-years at risk*.
Incidence rate of probable symptomatic dengue infection	All probable symptomatic dengue infection	Total person-years at risk*.
Proportion of subjects with primary inapparent dengue infection	All dengue IgG positive cases at the considered visit	Total number of IgG negative subjects at the previous visit
Proportion of subjects with secondary symptomatic dengue infection	All symptomatic infection since the previous visit	Total number of IgG positive subjects at the previous visit
Seroprevalence of dengue infection	All dengue IgG positive cases	Total number of subjects tested or previously positive

* Time at risk: In analyses by season the time at risk is calculated as the time from the visit scheduled before the season until the first event during the season, the next scheduled visit or the subject's withdrawal, whichever comes first.

In the analyses of all seasons combined the time at risk is calculated as the time from enrolment until the first event, the end of the study or the subject's withdrawal, whichever comes first.

CIs for incidence rates and proportions will account for clustering of observations within households for the analyses by centre and also the stratification by centres for the overall analyses. Details of the methods will be described in the SAP.

